7.3.3 EXTENDED WEAR Follow-up

Only subjects for whom the study doctor determined it was clinically appropriate to continue with the preferred device (either MLP or KTFS) will be invited to participate in the extended wear part of the clinical trial. The extended wear will involve about six months of home-use of the preferred device with a study visit at every one month period. More frequent monitoring visits may be requested by the study doctor based on clinical judgment. During the extended wear period, subjects may also receive REDCap survey link notifications each day to complete a brief survey to log if they are wearing the device. Please see section 7.3.7 for procedures that will be conducted at follow up visits.

7.3.4 Final Study Visit

At the final study visit (at the end of the extended wear) a clinical decision will be made as to whether or not the MLP or KTFS is recommended for continued use. Participants will be allowed to take the preferred device (MLP or KTFS) and continue wearing it, if considered clinically appropriate, and transferred to the clinical practice of the PI.

7.3.5 Long-term follow up: 6 and 12-month telephone follow ups

All subjects will be called at 6 & 12 months after the final study visit to complete some of the same questionnaires from earlier in the study (regardless of participation in extended trial). If subjects had continued using the device after the final study visit, the study staff will also ask them about device use & abandonment.

7.3.6 Early Termination Visit

In the event a participant is terminated from the study due to an Adverse Event, the study PI will follow the participant for at least 30 days after termination to confirm the event has resolved or the patient is receiving appropriate treatment.

7.3.7 Schedule of Events Table

*Visits 8-10 are in office, approximately every second week. There will be video

		Consent	EQ-5D-5L Questionnaire	aQoL Questionnaire	GBI Questionnaire	Visual Acuity	SlitLamp, skin rating, & NEI grading	Video Recordings & Comfort ratings	Application & Removal training	Debrief and device comparison questionnaire	Clinical decision
Device 1	Visit 1	x	x	x		x	x	x	x		
	Visit 2					x	x	x	x		
		About 1 week wearing at home with video calls for safety monitoring and daily survey about wear time									
	Visit 3		x	x	x	x	x	x			
	Washout (about 2 weeks)										
Device 2	Visit 4		x	x		x	x	x	x		
	Visit 5					x	x	x	x		
		About 1 week wearing at home with video calls for safety monitoring and daily survey about wear time									
	Visit 6		x	x	x	x	x	x			
	End of crossover period										
	Phone call									x	
	Visit 7					x	x	x			x
	Start of extended wear trial (about 6 months)										
Chosen device											
	Visit 8		x	x	x	x	x	x			
	Long term follow up										
	6 month phonecall		x	x	x						
	12 month phonecall		x	x	x						

call follow ups on weeks without an in-office visit

7.5 Concomitant Medications, Treatments, and Procedures

Oral and ophthalmic concomitant medications will be reviewed and recorded to confirm the patient does not have any systemic disease that would interfere with the study assessments and or data.

7.5.1 Precautionary Medications, Treatments, and Procedures

None.

7.6 Prohibited Medications, Treatments, and Procedures

Ophthalmic ointment or skin ointment applied near the eyes interferes with adhesion of the lid magnet and will need to be discontinued at least 1 day prior to the study. Patients may continue with artificial tears.

7.9 Participant Access to Study Agent At Study Closure

If considered clinically appropriate, participants will be allowed to take the MLP and continue wearing it after completion of the study, or to continue with the KTFS after completion of the study. MEEI has already approved provision of the MLP to non-research subject patients under the Humanitarian Devices rules, and Kinesio Tape is commonly used as a treatment for ptosis.

7.10 Virtual Visits

REDCap consent module will be used to obtain econsent.

In 2022, the NIH provided a supplement to allow virtual enrollment of up to 10 participants to help meet enrollment goals while promoting greater diversity of the study sample. Study procedures will be identical to those described in section 7.3, but will be conducted virtually via video visit. Methods for virtual monitoring of active participants during the pandemic related shutdown were developed and successfully implemented during the in 2020, as described in prior sections. The key differences and logistical solutions needed for entirely remote participation are summarized here:

Prior to consideration for enrollment, candidates will be required to provide a copy of a complete eye exam by any licensed provider conducted within the 3 months prior to the pre-screening consent video visit. The first video visit will be for the pre-screening MMSE. A visual acuity paper chart, and supplies for corneal sensitivity testing will be mailed to candidates ahead of this first visit. Study activities will not begin until the second video visit, to allow time for participants to receive a study equipment package in the mail from us. The package will include device supplies, device application instructions, Burton lamp artificial tears and NaFl strips (for remote cornea exam), paper questionnaires, and instructions for downloading a visual acuity and external eye photography app. Everything described in section 7.3 will be done on the video visit platform including but not limited to training to self-apply the lid devices and video recording of blinking.

8 ASSESSMENT OF SAFETY

8.1 Specification of Safety Parameters

The safety of the study devices will be evaluated at every visit following the enrollment visit and will be defined by the incidence of related adverse events. Specifically, we will evaluate:

10. **Systemic safety:** Incidence and severity of systemic adverse events during the study (adverse events spontaneously reported or observed by the Research Assistant).
11. **Ocular safety:** Incidence and severity of ocular adverse events during the study (ophthalmic examination, adverse events spontaneously reported).

SAFETY CUTOFFS: Serious adverse events which would result in study suspension: Should visual acuity decrease more than 2 lines, worsening of corneal rating of more than 1.5 points or other ocular surface ratings more than 2 points, and comfort rating lower than 5/10; study activities will cease for at least 1 week and an adverse event report will be sent to the IRB. Corneal rating changes >1.5 points will be reviewed by the independent safety monitor at the Eye and Ear to determine if criteria for study suspension or dismissal are met, and when it may be possible to continue. Serious adverse events which will result in immediate dismissal from the study (and treatment) include: 1) development of a related corneal ulcer (as judged clinically by the independent safety monitor) with or without infiltrate or 2) broken skin on the eyelid (skin decompensation).

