1 KEY ROLES

Principal Investigator – Overall responsibility for all study related activities.

Co-investigator (clinical trial lead): Responsibility for randomized crossover clinical trial management.

Clinical Research Technicians- Responsible for consenting, enrolling and scheduling subjects. Also will collect, record and report all study data, and fit and train for the MLP device and the tape (KTFS) as a backup plan.

Physical Therapy Advisor: Training of clinical study staff and monitoring the quality of fitting for the KTFS.

Engineering research fellow: Responsible for: Assembling MLP devices and maintaining device logs

Independent safety monitor: Examine participants with adverse events and review all safety outcome reports.

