8.1.1 Definition of Adverse Events (AE)

Adverse Event (AE): Any untoward or unfavorable medical occurrence in a human subject, including any abnormal sign (for example, abnormal physical exam or laboratory finding), symptom, or disease, temporally associated with the subject's participation in the research, whether or not considered related to the subject's participation in the research.

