8.2 Classification of an Adverse Event

The Investigator will promptly review documented adverse events and abnormal findings to determine 1) if the abnormal finding should be classified as an adverse event; 2) if there is a reasonable possibility that the adverse event was caused by the study device(s); and 3) if the adverse event meets the criteria for a serious adverse event.

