8.2.2 Relationship to Study device

Clinical Trial to improve the magnetic levator prosthesis (MLP) including the development and testing of a novel adjustable force system and comparison to the Kinesio Tape frontalis sling (KTFS) Version 1

If an adverse event or serious adverse event is recorded the study PI will determine the relationship to the study device.

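### Section 8.1 defines device safety by related adverse events, against its own listed parameters, and the PI assigns relatedness with no stated criteria, masking or second assessor

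*Combined protocol and SAP*

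**What the plan says.** The lead sentence of Section 8.1 reads, up to its qualifying word: "The safety of the study devices will be evaluated at every visit following the enrollment visit and will be defined by the incidence of related". What it qualifies is adverse events. The same section then names two parameters to be evaluated: "Incidence and severity of systemic adverse events during the study" and "Incidence and severity of ocular adverse events during the study". Neither is limited to related events. Section 8.1.1 covers any untoward occurrence "temporally associated with the subject's participation in the research, whether or not considered related to the subject's participation in the research".

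Two judgements come before any count. Under Section 8.2 the Investigator is to "determine 1) if the abnormal finding should be classified as an adverse event", and also judges causality and seriousness. Section 8.2.2 then says: "If an adverse event or serious adverse event is recorded the study PI will determine the relationship to the study device".

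Section 1 gives an outside check: "Independent safety monitor: Examine participants with adverse events and review all safety outcome reports". Section 8.1 adds that this monitor judges whether a corneal ulcer is related and reviews corneal rating changes above 1.5 points. Section 10.4.4, headed Safety Analyses, describes image review, logs and quarterly reports. It specifies no adverse event table and no comparison between devices.

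**The concern.** A safety outcome should be fixed before the data are seen and should not depend on an opinion formed case by case. Here the lead sentence passes the outcome through a causality judgement. The person who decides is the PI, who belongs to the team that says in Section 2.2 that it described the MLP. The institution has a patent application on the device (Section 6.1.10). Lid irritation, dryness or corneal staining can plausibly be put down to the device or to the underlying condition, so the judgement leaves room for discretion.

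Section 2.2 says that the research is needed to confirm safety as well as relative efficacy, so readers will set the two devices side by side even though no formal comparison is planned. If only related events are tabulated, a difference in attribution cannot be told apart from a difference in harm.

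**Working it through.** The plan gives no adverse event rate, safety margin or safety test, so there is no figure to reproduce. The check is mainly a comparison of texts.

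**1. Which events count**

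| Place | Events covered |
|---|---|
| 8.1, lead sentence | related only |
| 8.1, systemic parameter | all systemic, with severity |
| 8.1, ocular parameter | all ocular, with severity |
| 8.1.1, definition | all, related or not |
| 8.4.1, IRB schedule | at least possibly related |
| 10.4.7.1, minor events | no relatedness limit |
| 13.2, IRB reporting | no relatedness limit |

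Two analysts could report different safety results and both claim to follow Section 8.1.

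**2. Who judges, and whether masked**

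- Section 8.2.2 names the PI. Section 8.2 asks for a reasonable possibility of causation, but no criteria for applying that standard are given, and no second assessor.
- Section 10.6.1 masks participants (as to which device is new), the primary-outcome assessors and the primary-outcome analyst. It lists no safety assessor.
- The PI's masking status is not stated. It is very likely absent: the devices look different (spectacles with a lid magnet against tape), the PI places the tape under the backup plan in Section 10.6.1, and Section 10.4.4 has the PI reviewing images and possibly examining participants.

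**3. What a related-only count could do (illustration, assumed inputs)**

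Reported incidence = p × a, where p is the true all-cause incidence (set equal on both devices) and a is the share of affected participants whose event is called related. Take a = 1 on one device and a lower share on the other:

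| p | a = 0.75 | Difference from p | a = 0.50 | Difference from p |
|---|---|---|---|---|
| 20% | 15% | −5 points | 10% | −10 points |
| 40% | 30% | −10 points | 20% | −20 points |
| 60% | 45% | −15 points | 30% | −30 points |

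Section 10.5 gives a final sample size of 16 for the primary outcome. At p = 40% and a = 0.50, the expected numbers are 16 × 0.20 = 3.2 against 16 × 0.40 = 6.4 participants. One reclassified participant moves an incidence by 1/16 = 6.25 points. If the shares are equal the difference is p × a − p × a = 0. If the lower share falls on the other device, the sign reverses.

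**The case against.** The case against a stronger claim is good, and most of it stands.

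- A reader might infer that the plan counts only related events. The lines directly below the lead sentence, and Section 8.1.1, say otherwise. The finding is a contradiction to be reconciled.
- A reader might infer a safety comparison tilted in the MLP's favour. No between-device comparison is specified, safety is not among the outcomes in the Protocol Summary, and nothing shows the direction of any bias. The attribution shares above are assumed.
- A reader might take the PI's lack of masking as stated. It is a sound inference only. Section 16 also requires conflict-of-interest disclosure.
- A reader might infer that events judged unrelated escape oversight, because every category in Section 8.4.1 is a related one. Sections 10.4.7.1 and 13.2 report events to the IRB without that limit, and the Section 8.4.1 threshold includes events that are only possibly related.
- Harms of the eye surface and lid are also captured without attribution. The schedule in Section 7.3.7 has slit-lamp, skin, NEI and comfort ratings at all six crossover visits. The suspension cutoffs and the broken-skin criterion in Section 8.1 carry no relatedness condition, and Section 10.4.4 requires a second clinically trained image reviewer.

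These safeguards protect participants and preserve data. None of them says which events make up the reported safety outcome, and that point survives.

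**Conclusion.** The concern holds in a limited form. Section 8.1 contradicts itself and Section 8.1.1 on the safety outcome, and its lead sentence makes that outcome depend on a causality judgement by the PI with no stated criteria, masking or second assessor. This is a risk of differential attribution. The documents give neither its direction nor its size, and the illustration runs from no difference, if attribution is equal, to 30 points under the most extreme assumptions tried. It matters only if the lead sentence is followed when results are reported. With about 16 participants, a few judgements could then shape the result. This is a cheap improvement to the plan. It does not touch the primary efficacy analysis, the sample size or any clinical rule.

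**What to change.** 1. In Section 8.1, delete *related* from the definition, so that the safety outcome is the incidence and severity of all adverse events, in agreement with Section 8.1.1.
2. In Section 10.4.4, specify a table of all adverse events by the device in use at onset, with washout events shown separately and related events as a secondary listing.
3. Summarise the scheduled slit-lamp, skin, NEI and comfort ratings by device. They do not depend on attribution, nor on the prior decision under Section 8.2 about whether a finding is an adverse event, which the first two changes leave in place. They are not stated to be masked, and the report should say so.
4. Where the independent safety monitor has already given a view on relatedness, show it beside the PI's. Moving every causality judgement to the monitor is not needed: it would be new work, and nothing says that the monitor is masked.

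The cost is a few words, one or two extra tables and no new visits. The downside is higher headline rates, because unrelated events are included.

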Risk 2, reduced blink reflex: If the fitting of the MLP is not ideal, it is possible that participants (children and adults) would experience slowed or incomplete blink reflex. There is the potential that this could cause reversible ocular surface drying and discomfort. Participants, parents, and involved caregivers will be given specific instruction on how identify problems and when to remove the MLP. To summarize, they will be instructed to ask themselves at regular intervals “what is my level of comfort on a scale of 1-10” and if it is lower than 5 to remove the MLP and contact the study staff to schedule a visit to investigate. It is also possible that a reduced blink reflex could elevate the risk of foreign body in the case of projectiles. All participants will be fitted with safety grade or polycarbonate lenses, in their prescription (or non-prescription plano if they require none). Participants will be instructed to wear additional protective eyewear and to avoid places like machine shops where there could be metal shavings. The lid magnets are not strong enough to propel a magnetic/metal object towards the eye and the magnets should actually reduce the risk for metallic foreign body projectile entering the eye by redirecting it towards the spectacle magnet; however, there is risk that metal shavings could accumulate around the magnets if the device is

Clinical Trial to improve the magnetic levator prosthesis (MLP) including the development and testing of a novel adjustable force system and comparison to the Kinesio Tape frontalis sling (KTFS) Version 1

used in a situation such as a workshop where shavings are present. While these would not be projected into the eye, minor injury may result if the shavings get around the eye and then are rubbed into or sprinkle into the eye(s). Standard safety goggles will fit over the spectacles and participants will be informed that they should be worn as they normally would.

Risks related to KTFS taping:

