5 STUDY RECRUITMENT, ENROLLMENT AND WITHDRAWAL

Patient Gateway for recruitment will be utilized.

5.1 Participant Inclusion Criteria:

1. Presence of Blepharoptosis for at least one eye which occludes the visual axis in the resting state (no frontalis drive),
2. Moderate cognitive function or better defined as greater than or equal to 18 out of 30 on a pre-screening of the Mini-Mental State Exam.

3. Age 5 or older. (Children need to be included because they represent an important target population (pediatric neuro-muscular conditions), and because facial structure and skin characteristics may result in a different response than adults)

5.2 Participant Exclusion Criteria:

1. Absence of ptosis which occludes the visual axis
2. Presence of a corneal ulcer of any size, unless managed with a protective contact lens or other method and permission is granted from the candidate's managing eye doctor.
3. Age less than 5,
4. Severe Cognitive impairment defined as MMSE score <18, behaviors consistent with delirium (combinations of disorientation, hallucinations, delusions, and incoherent speech), or lethargy.
5. Presence of corneal hypoesthesia unless cleared for enrollment by a cornea or contact lens specialist;
6. Orbicularis weakness on the side of the ptosis.
7. Mechanical ptosis, including ptosis due to orbital or lid tumor, cicatricial processes affecting the movements of the upper lid, and exophthalmos.
8. Previous ptosis surgery less than 3 months prior to Visit 1.
9. Lid position affected by lid or conjunctival scarring.
10. History of herpes keratitis.
11. Periocular neurotoxin (eg, Botox, Xeomin, Dysport, Myobloc) injections on the side of the ptosis within 3 months prior to Visit 1 and during the study.
12. History of hyperthyroidism or thyroid eye disease (ie, exophthalmos, upper eyelid retraction, diplopia secondary to extraocular muscle involvement). Hypothyroidism that is controlled on medication is allowed.

Hypoesthesia and chronic corneal ulcers may be treated successfully, usually with artificial tears and/or a protective contact lens. Therefore, when there is hypoesthesia or chronic epithelial defect the PI will contact the candidate's cornea or contact lens specialist (e.g. via email or EMR message (EPIC)), and request permission to enroll the candidate. If they do not have a cornea or contact lens specialist, a consult with one at MEE who is not affiliated with the study will be requested prior to enrollment.

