7 STUDY PROCEDURES AND SCHEDULE

7.1 Study Procedures/Evaluations

7.1.1 Study specific procedures

The following procedures will be performed as part of the study (see schedule of events table in section 7.3.7.)

1. Refraction (if needed)
2. Visual acuity
3. Slit lamp examination of external eye, lid and cornea with Nafl & NEI scale
4. Comfort rating
5. Video recording of eye blinks
6. Rating of skin integrity
7. EQ-5D-5L questionnaire
8. GBI questionnaire
9. aQoL questionnaire

Based on experience, we anticipate that the first study visit will typically last about 120 minutes and subsequent visits about 60 minutes.

Some of the visits will be conducted virtually (as detailed in subsequent sections). To facilitate virtual visits, a visual acuity chart will be given to the subject to allow this safety outcome monitoring remotely and other safety outcomes will be conducted during the call (comfort scale, inspection of the external eye and lid skin).

Detailed plan for REDCap text message and email communication:

A short three-question survey will be used to document whether subjects are wearing a device during the periods of home use. Consent to receive a survey link by text message or email will be documented in the consent form along with the preferred contact method (text, email, or both). For subjects that consent to receive the survey links, their preferred phone number and/or email address will be recorded on a sheet separate from the consent form, which will be kept in a locked cabinet in a locked office. As soon as the phone number and/or email address have been input into REDCap, the original will be shredded.

Subjects who consent to receive the survey links will receive a text message or email (based on their communication preference) with a link to a REDCap survey twice daily when using one of the devices at home during the trial week. Please see uploaded document for details of the survey language and questions. Subjects will be able to decline receiving the survey links at any time.

Text message plan: Text messages will be sent to subjects using the Twilio platform. The “Survey as webpage” option will be selected so that subjects can access the REDCap survey URL directly from the text. Subjects’ phone numbers will only be entered if they consented to receiving messages in this way. A sentence in the text message will notify the subject that they can opt out of receiving these texts by replying “Stop”.

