7.3.2 CROSSOVER

After consent and enrollment, subjects will be randomly assigned to one of the two arms for the crossover period. In one arm subjects will receive the MLP first and the KTFS second. In the other arm, subjects will receive the KTFS first and the MLP second.

Each period of the crossover will last for about three weeks, including about two weeks of training in how to apply and remove the device followed by about one week of using the device at home. Training will be conducted at study visits at Mass Eye and Ear. Typically there will be two training visits. Baseline measures of eye lid blinking without and with the device will be taken during training. For the MLP, two baseline measures of eye lid blinking will be recorded one with the real MLP device and one with a sham MLP device to determine how much improvement might occur simply through a placebo effect. However, for the KTFS it will not be possible to take a baseline measure with a sham KTFS. Only subjects and caregivers who demonstrate sufficient ability to apply and remove the device will be permitted to take it home. During the period of home wear, there will be a video call every other day to monitor the subject’s use of the device and safety. During the kfts arm, an occupational or physical therapist consulting with the Massachusetts eye and ear study team may talk with the subject during the video conference call to ensure that the kinesio tape is in the correct position. Mass General Brigham approved software will be used for video calls. During the trial week of home use of devices, subjects will

also receive REDCap survey link notifications each day to complete a brief survey to log if they are wearing the device (see the detailed plan above, and see attached document for survey language and questions).

To ensure no carry-over effects, there will be a washout of about 2 weeks duration between the first and second period of the crossover during which subjects will not be permitted to use any device for their blepharoptosis. (This will be similar to their habitual state before enrollment since none of the participants would have been using any device for their blepharoptosis about two weeks before enrollment).

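### Section 8.1 joins low comfort to the objective safety cut-offs with *and*, so read literally no objective sign alone requires the pause and IRB report

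*Combined protocol and SAP*

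**What the plan says.** The pause rule is one sentence of section 8.1. It opens with "Should visual acuity decrease more than 2 lines, worsening of corneal rating of more than 1.5 points" and runs on to "or other ocular surface ratings more than 2 points, and comfort rating lower than 5/10; study activities will cease for at least 1 week". An adverse event report to the IRB follows from the same sentence.

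The next sentence sends corneal changes above 1.5 points, with no comfort condition, to the independent safety monitor, whose task is "to determine if criteria for study suspension or dismissal are met, and when it may be possible to continue". A related corneal ulcer or broken eyelid skin means dismissal whatever the comfort score.

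Three other places bear on the rule:

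- Section 5.2 lists as an exclusion "Presence of corneal hypoesthesia unless cleared for enrollment by a cornea or contact lens specialist", so people with reduced corneal sensation can enter once cleared.
- The text on reduced blink reflex (Risk 2) tells MLP users to rate their own comfort "and if it is lower than 5 to remove the MLP and contact the study staff to schedule a visit to investigate".
- Section 7.3.2 states: "During the period of home wear, there will be a video call every other day". For remote contacts, section 7.1.1 says "a visual acuity chart will be given to the subject to allow this safety outcome monitoring remotely". The other items listed for the call are comfort and a look at the outer eye and lid skin. No corneal grade is listed.

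**The concern.** A written cut-off exists so that action does not depend on judgement in the moment. Here the sentence can be read in more than one way, and its literal reading is the less protective one: a symptom must accompany the sign.

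That is weakest where symptoms are least reliable. Reduced corneal sensation may keep the comfort score high while the surface deteriorates. The documents do not say this; it is a clinical inference, but a direct one. The hazard itself is one the protocol names: incomplete or slowed blinking with surface drying for the MLP, and drying for the tape.

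The IRB report depends on the same sentence. If the rule is not met, an event that is related, expected and not serious goes to the IRB only once a year under section 8.4.1.

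**Working it through.** The plan gives no figure to reproduce. The check is one of logic, followed by a look at when the rule can act.

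**Inputs (section 8.1).** A = acuity down more than 2 lines; C = corneal rating worse by more than 1.5 points; S = other surface ratings worse by more than 2 points; F = comfort below 5/10. C and S are joined by *or*. F is joined by *and* after a comma, which speaks against tying it to S alone.

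**Counting patterns.** Four yes/no items give 2^4 − 1 = 15 patterns with at least one cut-off crossed. With F absent, 2^3 − 1 = 7 patterns have at least one objective cut-off crossed. On a home call only A and F are clearly scored, giving 2^2 − 1 = 3 patterns. If the external inspection is also scored as S, which is not stated, there are 2^3 − 1 = 7.

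| Reading | All 15 | Comfort 5 or above (7) | Call: A, F (3) | Call: A, S, F (7) |
|---|---|---|---|---|
| A and (C or S) and F | 1 × 3 × 1 = 3 | 0 | 0 | 1 |
| (A or C or S) and F | 7 × 1 = 7 | 0 | 1 | 3 |
| A or C or S or F | 15 | 7 | 3 | 7 |

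Under both *and* readings F is necessary, so the third column is zero.

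**Does another provision close the gap?** The monitor's review needs no low comfort, but it covers only C, and it asks whether the suspension or dismissal criteria are met. That returns the monitor to the same sentence. A and S have no such route. Dismissal for an ulcer or broken skin acts after the harm that a pause is meant to prevent. The Risk 2 instruction acts on F alone, so it does not help when F is absent.

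**When does the wording change what happens?** Following the schedule in section 7.3.7:

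- *Visits 2 and 5*: acuity, slit-lamp grading and comfort are all taken and the home week follows. The wording matters here.
- *Home calls*: it matters for acuity, and for surface ratings only if the inspection is scored. It does not matter for the cornea, which these calls do not grade.
- *Visit 3*: a washout of about 2 weeks without any device follows (section 7.3.2), which exceeds the 1-week minimum pause. Only the report is affected.
- *Visit 6*: the crossover ends. Visit 7, with slit-lamp examination and a clinical decision, comes before any extended wear.
- *Extended-wear visits*: wear is continuing, so the wording matters.

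**The case against.** The strongest reply is that separate triggers were plainly intended. The list is introduced as events, in the plural, and *and* before the last item of a list is ordinary usage. Sending corneal change alone to the monitor would make little sense if it could never be enough, and asking when the participant may continue implies an interruption. Risk 2 acts on comfort alone. This is persuasive as to intent, but it does not make the sentence say so. Where the protocol wants any single item to count, it can state that outright, as in the definition of a serious adverse event in section 8.1.2.

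The second reply is that discretion fills the gap. The investigator may discontinue a participant for any safety concern (section 5.4.1), abnormal findings are reviewed promptly (8.2), the PI reviews adverse events within 24 hours (8.4.1), and extra visits may be requested in extended wear (7.3.3). Hypoesthesia requires specialist clearance beforehand. These safeguards are real and limit the consequence. None makes a pause mandatory.

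The third reply is that reduced sensation is not absent sensation, and a general comfort question can pick up lid or skin discomfort. That also stands, and it is why the score *may*, not will, stay high.

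**Conclusion.** The point holds as a drafting fault in a safety decision rule. Read literally, section 8.1 requires a symptom before an objective sign leads to the pause and report: 0 of 7 patterns with comfort at 5 or above, against 7 of 7 under an any-one rule. These are counts of logical patterns and say nothing about how often each occurs. The number enrolled with hypoesthesia is not given. The effect of reduced sensation on the comfort score is an inference. The text between section 2.2 and Risk 2 was not available, so any monitoring rule there could not be checked.

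Three stronger readings are not supported:

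- A reader might infer that participants with hypoesthesia are unprotected. Monitor review of corneal change, the dismissal rules, discretionary withdrawal, the washout and the Visit 7 decision all operate without low comfort.
- A reader might blame this word for corneal damage going unnoticed between slit-lamp visits. Those intervals come from the visit schedule and from the lack of a corneal grade on the calls; rewording would not shorten them.
- A reader might suspect that lid elevation hides true acuity loss on home readings. The documents give no device condition or size for such an effect, and it may be zero.

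The correction should be made. It is a modest one and does not touch the efficacy analysis plan.

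**What to change.** Reword the sentence in section 8.1 along these lines:

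*Study activities are paused for a minimum of 1 week, and an adverse event report goes to the IRB, if any one of the following occurs: (a) acuity down by more than 2 lines; (b) corneal rating worse by more than 1.5 points; (c) any other ocular surface rating worse by more than 2 points; (d) comfort below 5/10.*

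The monitor's review can stay as written, because the criteria it refers to would then be clear. No visit or procedure is added.

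The costs are a few more pauses and IRB reports. Some will be for comfort alone, which section 10.4.7.1 might otherwise treat as a minor event reported annually. A pause is at least as long as the home-wear week, so now and then a 1-week reading will have to be rescheduled. It should be moved, not left missing and filled from T1 or T0 under section 10.2 (taking T2 there to be the 1-week reading).
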